9.4 Telephone contacts

Telephone Contact #1 (Visit #3)- The research coordinator will contact the participant after completion of the 150mg dose in order to determine adverse effects of medication and to monitor tolerance. The research coordinator will also administer the NIH-CPSI and SYM questionnaires (including the GRA question) over the phone.

Telephone Contact #2 (Visit #4)- The research coordinator will contact the participant after completion of the 300mg dose in order to determine adverse effects of medication and to monitor tolerance. The research coordinator will also administer the NIH-CPSI and SYM questionnaires (including the GRA question) over the phone.

9.5 Treatment Visit (Visit #5)

The participant will be required to return for a third clinic visit six weeks after treatment start. The primary efficacy measure is the CPSI.

- *Concomitant Medications.* The research staff will record the medications currently being taken by the participant. Participants will be asked to recall their medications if they fail to bring them to the second screening visit.
- *Adverse Events/Serious Adverse Events.* The research staff will record any adverse events that have newly occurred, changed, or been resolved.

- *Symptom Questionnaires.* As in the Screening/Randomization Visit (Visit #2), the participant will be required to complete a number of different questionnaires, with the addition of the single question GRA.

Unused study medications will be returned and the RC will do a pill count and assess drug compliance. The *Study Stop Form* and *Treatment Stop Form* will also be completed at this visit for those participants not continuing on to Phase II.

At this visit, sites that choose to will have the option of asking whether the participant is willing to provide a second urine and EPS specimen, provided that this additional procedure is specified in the site's informed consent.

9.6 Dose Taper Phase

The participant electing not to continue into Phase II will be provided with “taper down” instructions, beginning at week seven (7). The taper down will be completed in one week, with participants on 300 mg/day for the first three (3) days and then 150 mg/day for the remaining four (4) days. Participants who were only able to tolerate the 300mg/day dose will taper down for 4 days at 150mg/day. Participants who were only able to tolerate the 150mg/day do not need to taper down. The participant will be contacted by telephone at the end of week seven (7) to confirm completion of study drug taper (Visit #6). The Research coordinator will also continue to record the participant's concomitant medication use as well as monitor any adverse events that have newly occurred, changed, or been resolved. The NIH-CPSI will also be completed.

9.7 Phase II Study Continuation

At Visit #5, participants will be given the option of discontinuing study participation, or continuing on to the open-label phase of the study (Phase II) for an additional six (6) weeks. Those participants having a Serious Adverse Event in Phase I of the study will be ineligible for Phase II participation.

As in Phase I, there will be two telephone contacts (Visits # 7 and #8) after completion of the 150mg/day dose (1 week duration) and the 300 mg/day dose (1 week duration). Again, the research coordinator will administer the NIH-CPSI and SYM questionnaires (including the GRA question) over the phone.

At the end of the six (6) week Phase II treatment period, participants will return to the clinic for one last visit (Visit #9).

- *Concomitant Medications.* The research staff will record the medications currently being taken by the participant. Participants will be asked to recall their medications if they fail to bring them to the second screening visit.
- *Adverse Events/Serious Adverse Events.* The research staff will record any adverse events that have newly occurred, changed, or have been resolved.
- *Symptom Questionnaires.* As in the Screening/Randomization Visit (Visit #2), the participant will be required to complete a number of different questionnaires, with the addition of the single question GRA.

Study close-out will take place and include a pill count on returned study medications, drug compliance assessment, and completion of the *Study Stop* and *Treatment Stop* forms for all participants. Similar to the procedure in Phase I of the study, participants will be provided with drug taper instructions and contacted by telephone at the end of the week to confirm completion of the taper (Visit #10).

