6.2 Exclusion Criteria

Any participant satisfying any one of the following criteria will NOT be eligible to participate in the proposed randomized clinical trial:

1. Participant has continued evidence of facultative Gram negative or enterococcus with a value of ≥ 1000 and $\leq 100,000$ CFU/ml in mid-stream urine (VB2), as demonstrated by repeat culture obtained no less than seven (7) days post antibiotic treatment.
2. Participant has a calculated creatinine clearance of <60 mL/min.
3. Participant has a platelet count $<100,000/\text{mm}^3$.
4. Participant is allergic to antiepileptic/antiseizure medications.
5. Participant has a known allergy or sensitivity to pregabalin (Lyrica®).
6. Participant is taking thiazolidinedione antidiabetic agents (i.e. rosiglitazone and pioglitazone).
7. Participant has New York Heart Association Class III or IV congestive heart failure.
8. Participant has a history of thrombocytopenia, or a bleeding diathesis.
9. Participant has a history of prostate, bladder or urethral cancer.
10. Participant has a history of alcohol abuse.
11. Participant has inflammatory bowel disease (such as Crohn’s disease or ulcerative colitis, but not irritable bowel syndrome).
12. Participant has undergone pelvic radiation or systemic chemotherapy.
13. Participant has undergone intravesical chemotherapy.

14. Participant has been treated with intravesical BCG.
15. Participant has unilateral orchalgia without other pelvic symptoms.
16. Participant has an active urethral stricture.
17. Participant has a neurological disease or disorder affecting the bladder.
18. Participant has a neurological impairment or psychiatric disorder preventing his understanding of consent and his ability to comply with the protocol.

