7.4 Concomitant Medications

7.4.1 Drug Interactions:

Pregabalin is not metabolized by the liver, does not affect the cytochrome P450 system nor is bound to plasma protein and therefore does not have drug-drug interactions from these mechanisms.⁹ No evidence of pharmacokinetic drug-drug interactions has been observed or reported. However, pregabalin appears to potentiate or be additive in the impairment of cognitive and gross motor function caused by oxycodone, ethanol, and lorazepam²². Similarly, concomitant use of the thiazolidinedione class of antidiabetic drugs could be additive in leading to weight gain and fluid retention.

7.4.2 Exclusionary medical condition:

Renal excretion is the primary route of pregabalin elimination; 98% of the administered dose is eliminated as unchanged drug in the urine.¹⁷ Therefore, significant impairment of renal function could lead to higher pregabalin blood levels.²³

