8.3.1 Risks of pregabalin

Common Side Effects: Dizziness, somnolence and peripheral edema (mainly of the lower limb) of mild-to-moderate intensity are the most frequently observed adverse events, and appear to be dose-dependent. The incidences of dizziness were 12% and 28% with pregabalin 150 mg/day and 300mg/day (vs.15% with placebo),⁸ and 28% with pregabalin 600 mg/day (vs. 12% with placebo).¹⁴ The incidences of somnolence were 15% and 24% with pregabalin 150 mg/day and 300mg/day (vs.7% with placebo),⁸ and 25% with pregabalin 600 mg/day (vs. 7% with placebo).¹⁴ The incidences of peripheral edema were 3% and 13% with pregabalin 150 mg/day and 300mg/day (vs. 0% with placebo),⁸ and 19% with pregabalin 600 mg/day (vs. 2% with placebo).¹⁷ Other common events include dry mouth, asthenia, amblyopia, thinking abnormal, and weight gain.²²

Weight Gain and Peripheral Edema: Pregabalin treatment caused weight gain. Although weight gain was not associated with clinically important changes in blood pressure in short-term controlled studies, the long-term cardiovascular effects of pregabalin-associated weight gain are unknown. There is also limited data on congestive heart failure patients with New York Association Class III or IV cardiac status. Pregabalin treatment also caused edema, primarily described as peripheral edema. Concomitant use of pregabalin and drugs that can cause additional weight gain and/or fluid retention, such as the thiazolidinedione class of antidiabetic drugs, could have an additive effect and possibly exacerbate or lead to heart failure, especially in patients with preexisting cardiac conditions.²²

Platelet Count: In clinical studies, decreases in platelet counts were observed more frequently with pregabalin than with placebo; however these changes were not associated with events that could indicate changes in platelet or overall hemostatic function.²²

Renal: Pregabalin is associated with an elevation in creatinine kinase levels in some patients. Review of individual patient cases does not suggest a clinically important risk of renal dysfunction associated with these elevations. Pregabalin had no apparent effect on liver and renal function.²²

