9.3 Screening/Randomization Visit (Visit #2)

This second screening visit should be completed at least two (2) days after, but no more than four (4) weeks after Visit #1. Participants who still meet all eligibility criteria at this visit will complete the questionnaires described below, and will continue on to randomization. During this clinic visit, the participant will have an opportunity to ask questions and express concerns related to the study.

- *Eligibility Checklist.* An eligibility checklist confirming that the participant still meets all eligibility criteria will be completed by the RC prior to randomization.
- *Concomitant Medications.* The research staff will record the medications currently being taken by the participant. Participants will be asked to recall their medications if they fail to bring them to the second screening visit.
- *Adverse Events/Serious Adverse Events.* The research staff will record any “pre-existing conditions,” as defined in the Manual of Procedures (MOP).
- *Review VB2 Culture Results.* The research staff will review culture results from the baseline visit to determine participant eligibility. Participants will be excluded from the trial if they have continued evidence of facultative Gram negative or enterococcus with a value of ≥ 1000 and $\leq 100,000$ CFU/ml, as demonstrated by repeat culture obtained no less than seven (7) days post antibiotic treatment.
- *Review Creatinine Clearance Measurement.* The research staff will review lab results from the baseline visit to determine participant eligibility. Participants will be excluded from the trial if they have a calculated creatinine clearance value of <60 mL/min.

- *Review Platelet Count.* The research staff will review lab results from the baseline visit to determine participant eligibility. Participants will be excluded from the trial if they have a platelet count of $<100,000/\text{mm}^3$.
- *Symptom Questionnaires.* Each participant will complete the following symptom questionnaires at this visit and at the next Clinic visit:
 1. NIH-Chronic Prostatitis Symptom Index (NIH-CPSI)
 2. Symptom Assessment Form (SYM)
 3. MOS SF-12 Health Status Questionnaire (SF-12)
 4. McGill Pain Questionnaire (MPQ)
 5. Hospital Anxiety and Depression Scale (HADS)
 6. Sexual Health Inventory for Men (SHIM)
 7. Pain medication Questionnaire (PAIN)

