10.5 Participant Withdrawals

It is expected that some participants may drop out of the trial due to side effects or lack of efficacy prior to the six (6) week endpoint. However, all attempts will be made to get complete data on all participants, including those who cease treatment prior to six (6) weeks, in order to conduct the primary intent-to-treat analysis for secondary endpoints. It is expected that a maximum of 15% of participants will withdraw completely from treatment AND follow-up prior to six (6) weeks.

Under certain circumstances, a study participant may have his treatment terminated prior to the six (6) week clinic visit. These circumstances include: unacceptable concomitant medications/treatments, unacceptable adverse events as determined by the Principal Investigator (PI), participant dissatisfaction with treatment, or participant disinterest in continued study participation. In addition, any participant who acquires a serious or life-threatening medical condition while participating in the study may have the study treatment terminated early at the discretion of the PI. A participant may also undergo early study termination because of a change of residence outside the driving distance of the CPCRN-2 network.

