12.0 Statistical Considerations

12.1 Summary of Study Design

The proposed study design is a two-arm, double blind, randomized clinical trial (RCT) to evaluate the efficacy and safety of pregabalin, as compared to matching placebo. The primary endpoint on which sample size requirements are based is the comparison of response rates, with responder being defined in terms of a decrease in the NIH-CPSI total score as described in Section 2.6. The proportion of “responders” in each treatment arm will be compared, in an intent-to-treat analysis, to evaluate the overall efficacy of the active therapy as compared to placebo. Approximately 318 eligible participants, 212 in the active treatment arm versus 106 in the placebo arm, will be randomized and followed for a period of six (6) weeks after randomization for the primary, and all secondary endpoints analyses.

An open-label phase for this trial (Phase II) will be offered to all participants after completion of the initial six (6) weeks of treatment, with the exception of those having a Serious Adverse Event while on study treatment in Phase I. Participants on active therapy or placebo will be offered active therapy and followed for an additional six (6) weeks. Participants will remain blinded to their initial treatment assignment until the end of the open label phase. The Phase II study is for the purpose of evaluating long term treatment effect. The GRA, NIH-CPSI will be re-examined again at the end of the Phase II.

An overview of the design considerations and statistical analysis plan, including sample size and power considerations, is provided in the following sections. Additional details will be provided in the study Data Analysis and Monitoring Plan (DAMP), provided prior to study initiation.

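### Phase II entry is barred by rule only for a Phase I SAE, so a man who starts a thiazolidinedione during Phase I can be given the open-label kit although exclusion 6 would have refused him at week 0

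*Combined protocol and SAP*

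**What the plan says.** Section 9.7 gives the entry rule for the open-label phase: "Those participants having a Serious Adverse Event in Phase I of the study will be ineligible for Phase II participation". Section 12.1 gives the same rule: Phase II is "offered to all participants after completion of the initial six (6) weeks of treatment, with the exception of those" who had an SAE on Phase I treatment. Neither section names another bar, and neither refers to a check held in another document.

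Section 6.2 excludes men taking a thiazolidinedione (exclusion 6). Exclusion 7 reads: "Participant has New York Heart Association Class III or IV congestive heart failure". Both are applied at the two screening visits. Section 9.3 states: "An eligibility checklist confirming that the participant still meets all eligibility criteria will be completed by the RC prior to randomization". Appendix A schedules the eligibility checklist at Visits 1 and 2 only.

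Section 7.4.1 covers the drug class in one sentence: "Similarly, concomitant use of the thiazolidinedione class of antidiabetic drugs could be additive in leading to weight gain and fluid retention". It contains no prohibition. Section 7.4.2, on exclusionary conditions, deals only with renal function.

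The reason for caution is in section 8.3.1: pregabalin with drugs of this kind "could have an additive effect and possibly exacerbate or lead to heart failure", particularly where there is existing cardiac disease.

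**The concern.** The protocol refuses a man at week 0 because a named combination carries a cardiac risk. At week 6 it offers him active drug under a rule that does not ask about that combination. The reason for exclusion 6 is the same at both times. It applies most directly to a man who had placebo in Phase I, because the second kit is his first study exposure to pregabalin.

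The SAE bar cannot catch this case. Section 10.0 defines an adverse event as a sign, symptom or disease, and starting a prescribed drug is none of these. Because section 7.4 prohibits nothing, the combination can also run on within either phase.

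The matter at stake is participant safety in a few men. The sample size and the Type I error rate do not depend on it.

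**Working it through.** **Step 1. Who is stopped by rule at Visit 5?**

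| Event in Phase I | Refused at week 0? | Barred by 9.7 and 12.1? | Other cover |
|---|---|---|---|
| Starts a thiazolidinedione | Yes, exclusion 6 | No, not an adverse event | 10.5, discretionary |
| New Class III/IV heart failure, classed as an SAE | Yes, exclusion 7 | Yes | Not needed |
| New Class III/IV heart failure, not classed as an SAE | Yes, exclusion 7 | No | 10.5, discretionary |

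The third row is narrow. The SAE definition in 10.1 takes in hospitalization, significant disability and important medical events by judgment. The first row carries the point.

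**Step 2. Are the data for a check already collected?** Appendix A schedules the concomitant medication and adverse event forms at Visits 2 to 10. After randomization the on-drug contacts are Visits 3, 4 and 5 (weeks 2, 4, 6) and Visits 7, 8 and 9 (weeks 7, 8, 12), six in all. The dispensing log is also completed at Visit 5. No new test or visit is needed.

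**Step 3. How much overlap does a Visit 5 bar remove?** The plan gives no figure of its own to reproduce. Inputs:
- Phase I lasts 6 weeks and Phase II lasts 6 weeks (7.1, 7.2), 12 in total.
- Allocation is 2:1, 212 to pregabalin and 106 to placebo (12.1).
- Assumptions: the thiazolidinedione is started at week w and continued to week 12; nobody acts under 10.5; taper of up to one week is not counted.

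For a start in Phase I, overlap with pregabalin under the stated rule is 12 − w for a man randomized to pregabalin. It is 12 − 6 = 6 for a placebo man, who has no pregabalin before week 6. A Visit 5 bar leaves 6 − w and 0 respectively.

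| Start | Phase I arm | Overlap, weeks | Left after Visit 5 bar | Removed |
|---|---|---|---|---|
| Week 1 | Pregabalin | 12 − 1 = 11 | 6 − 1 = 5 | 6/11 = 55% |
| Week 1 | Placebo | 6 | 0 | 6/6 = 100% |
| Week 1 | 2:1 average | (2×11 + 6)/3 = 9.3 | (2×5 + 0)/3 = 3.3 | 6/9.3 = 64% |
| Week 5 | Pregabalin | 12 − 5 = 7 | 6 − 5 = 1 | 6/7 = 86% |
| Week 5 | Placebo | 6 | 0 | 6/6 = 100% |
| Week 5 | 2:1 average | (2×7 + 6)/3 = 6.7 | (2×1 + 0)/3 = 0.7 | 6/6.7 = 90% |
| Week 7.5 | Either | 12 − 7.5 = 4.5 | 4.5 | 0% |

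The average percentages are mean weeks removed over mean weeks of overlap.

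**Step 4. What does a rule in 7.4 add?** Suppose it is acted on at the next scheduled contact. For a week-1 start in a pregabalin man, action at Visit 3 (week 2) leaves 2 − 1 = 1 week and removes 10/11 = 91%. For a start at week 7.5, action at Visit 8 (week 8) leaves 0.5 weeks and removes 4/4.5 = 89%. Only this rule reaches a man who starts the drug in Phase II.

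The longest interval without a scheduled contact is 12 − 8 = 4 weeks, which section 7.2 sets at 600 mg/day. Visit checks therefore need to be backed by an instruction to report.

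**The case against.** The strongest reply is that section 10.5 already deals with this. It says that "a study participant may have his treatment terminated prior to the six (6) week clinic visit", and concomitant medication judged unacceptable is one of the listed grounds. An investigator would read that ground in the light of exclusion 6 and section 8.3.1, and would see the medication record at Visits 3, 4 and 5. Phase II is offered only after six weeks of treatment, so a man stopped in this way would not enter. Section 10.5 also lets the investigator stop treatment for a serious condition acquired during the study. With the SAE definition in 10.1, that leaves little heart failure uncovered. Finally, sections 7.0, 7.1 and 11.1 defer detail to the Medication Manual and the Manual of Procedures, either of which could list prohibited drugs or require a dispensing check.

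Much of this stands. A reader might infer that nothing protects these men, or that heart failure in general goes unchecked; the documents support neither. What remains is that 10.5 is permissive, does not say which medications are unacceptable, and frames the medication ground as falling before the six-week visit. The stated entry rule in 9.7 and 12.1 points neither to 10.5 nor to a manual. Leaving this to judgment is out of step with a protocol that made the same matter an absolute exclusion at entry.

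**Conclusion.** The point holds as a gap in the stated rules, and it should be closed. Sections 9.7 and 12.1 admit to Phase II a man on a thiazolidinedione whom section 6.2 would have refused, and section 7.4 does not forbid the drug on study. The heart-failure case is secondary and narrow.

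The documents give no rate of new thiazolidinedione use or new heart failure, so no count of affected men can be given; it is likely small. The overlap figures describe one affected man under chosen start weeks and do not measure risk. They assume continued use and no action under 10.5. A reader might take 11 weeks as applying to every such man, but one third receive placebo in Phase I, which brings the week-1 average to 9.3.

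Two other inferences go too far. The gap does not threaten the trial's efficacy conclusion: the primary endpoint is at week 6 and section 12.9 keeps Phase II exploratory. Nor do the documents show a need to add an allergy bar to Phase II entry. Reactions to study drug are adverse events, which the SAE rule and the adverse-event ground in 10.5 can reach, and no defect there has been shown.

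Confidence is medium, mainly because the two manuals could not be seen.

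**What to change.** 1. In 9.7 and 12.1, add that exclusions 6 and 7 are rechecked at Visit 5 from the concomitant medication and adverse event records, before the second kit is dispensed, and that a man meeting either is ineligible for Phase II. Treatment is masked, so the check applies to all men alike.
2. In 7.4, state that thiazolidinediones are not permitted while on study drug in either phase. Men should be told to report before starting one, so that another antidiabetic agent can be considered. If one is started, study drug is tapered and stopped, and follow-up continues under 12.4.

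The cost is one clause each in 9.7 and 12.1 and a short addition to 7.4, with no new test, form or visit. There will be slightly fewer entrants to an exploratory phase and an occasional early stop of study drug in Phase I. It would be too strong to say that the primary comparison is untouched: a pregabalin man stopped early may give his week-6 NIH-CPSI off drug and, kept in the intent-to-treat analysis, would dilute the contrast slightly. With so few men expected, that dilution should be negligible at most.
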